## STUDY CALENDAR\*

Treatment plan:	Prior to Treatment		Days on Study Treatment										Off
	Screening	Baseline (Day 0)**	8	28	90	180	270	365	455	540	630	730	738
STUDIES													
Primary Cancer Treatment History	X												
General History and Physical	X											X	
Health Assessment						X		X		X		X	
Breast Evaluations													
Clinical Breast Exam	X					X		X		X		X	
Breast Imaging a	X							X				X	
Breast Tissue Sampling b		X										X	
Blood/Urine Tests													
CBC and Metabolic Panel c	X							X				X	
PT/PTT (pre-RPFNA)	X											X	
Beta-Human Chorionic Gonadotropin ( $\beta$ -HCG), if needed d	X												
FSH level, if needed e	X												
Blood for circulating biomarkers f		X						X				X	
Fasting lipid profile g		X						X				X	
Anti-thrombin-III h		X						X				X	
Blood and urine to assess bone turnover i		X						X				X	
Self-Administered Questionnaires													
Demographics and BC risk Form j	X												
Family History Form j	X												
NSABP Quality of Life Form j		X				X		X		X		X	
Treatment Management													
Study tablet dispensal k		X			X	X	X	X	X	X	X	X	
Study tablet collection m						X		X		X		X	
Symptom log j		X		X	X	X	X	X	X	X	X	X	
Adverse Event Collection Form j						X		X		X		X	
Follow up phone call l			X	X	X		X		X		X		X

a Annual mammograms will be required as standard of care follow-up for this patient population per COG cancer survivorship or NCCN guidelines. For patients who are at least 8 years beyond their RT exposure, annual screening breast MRIs are recommended. Both forms of breast imaging will be timed to the menstrual cycle and submitted electronically as described in section 11.1.1.

b Will be done via RPFNA described in section 11.2, for patients consented prior to protocol version 3/9/2015 and discontinued for all participants 10/26/15.

c Platelet count should be included in the CBC panel, differential is not needed. The metabolic panel should include liver function tests.

d Only if premenopausal with irregular menstrual cycles, to rule out pregnancy (see eligibility criteria).

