### 10.3 Parameters to be Measured During Treatment

All evaluations will be measured per the study calendar schedule using the assay methodology outlined in Section 11.0. Analysis of results is fully described in Section 12.0.

The following are biological response endpoints:

1. Mammographic Breast Density
2. Tissue biomarkers of BC risk – Cytomorphology, proliferative (Ki67) index, and apoptotic (caspase) index
3. Insulin Growth Factors – IGF-1 and IGFBP-3

The following endpoints are measures of safety and tolerability:

1. Bone metabolism markers - serum bone specific alkaline phosphatase (BSAP) and urine N-telopeptide crosslinks (NTX)
2. Fasting lipid panel – total cholesterol, HDL-cholesterol, LDL-cholesterol, and triglycerides
3. Clotting propensity – anti-thrombin III (AT-III)
4. Symptom logs

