#### Patient reported symptoms and adherence to the chemopreventive agent:

The National Surgical Breast and Bowel Project (NSABP) developed a standardized quality of life (QOL) questionnaire to assess patient reported symptoms in response to hormonal interventions, which they used in the NSABP P-1 and P-2 breast cancer prevention trials (**NSABP QOL questionnaire**). The most recent version of this questionnaire, which was used in the NSABP P-2 trial [101], will be used. The salient domains captured by this questionnaire include both physical and mental well-being. In addition, a **Symptom Log** including the **HEAL hormone-related symptoms instrument** will be used [102]. This questionnaire captures general symptoms along with specific hormone-related symptoms along the following scales: vasomotor, vaginal, incontinence, cognitive/mood, and weight gain/appearance. Both questionnaires will be administered at baseline and during the two-year treatment period according to the study calendar. Pill counts will also be used to determine adherence to the prescribed intervention using the **Adherence Tracking Form**.

Patients who report intolerable hot flashes may be managed with any of the following interventions (please refer to the **Treatment and Follow-up SOP** for recommended algorithm):

- Vitamin E 800 IU po daily
- Effexor (venlafaxine) XL 37.5-75 mg po daily

- Neurontin (gabapentin) 300mg po TID
- Lyrica (pregabalin) 75mg po BID

Patients who report vaginal atrophic symptoms may be managed with any of the following interventions (please refer to the [Treatment and Follow-up SOP](#) for recommended algorithm):

- Replens
- Astroglide
- Vagifem
- Estring

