**Subjective safety and tolerability measures:**

**Treatment adherence.** Compliance will be measured by pill counts performed every 3 months. The number of pills taken out of the total prescribed in a 3-month period will be modeled as a random effects binomial regression model [105]. The binomial rates from 8 time points (month 3 to 24) will be modeled as unstructured mean model with 7 indicator variables as well as polynomial models over time. The random-intercept and the random intercept and slope models will be considered. The significance of the time indicators or parameters by treatment interaction will be evaluated for treatment difference in compliance.

Voluntary withdrawals will be examined at the end of the study by comparing the percent of withdrawals between the treatment groups using a chi-square test or Fisher's exact test.

**Patient reported symptoms.** The outcomes will be scored as a 5-point Likert-type scale (0 to 4) in response to questions on how much the patients are bothered by certain symptoms. The questionnaire will be administered every six months, for a total of five time points. The responses will be treated as normally distributed, as ordinal or dichotomized variable, and we will apply the linear mixed effects model or GLMM methods to compare changes between treatment groups. Because of additional time points available, in addition to the unstructured mean model, we will also fit piecewise models with join point at 6 months, considering linear and curvilinear trajectories between 6m and 24m time points.

***Exploratory Aim 1: To examine the modifying effects of demographic, clinical, and molecular characteristics on both efficacy and safety markers.***

As the primary aim of this trial is to examine the main effects of low dose tamoxifen treatment on MBD, we will examine the modifying effects of demographic, clinical, and molecular characteristics as exploratory analysis. Even if time by treatment interaction (main treatment effect) is not significant, examining the modifying effects of covariates may reveal subgroups that respond differently to low dose tamoxifen. A three-way interaction of time by treatment by modifying variable will be included in the longitudinal model containing a two-way time by treatment group interaction. Modifying effects will be considered statistically significant if the three-way interaction is significant. The covariates of interest are described below.

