#### C. Molecular characteristics.

The following variables are known to influence efficacy of tamoxifen in the treatment of BC patients and will be analyzed at a later date.

*Endoxifen levels* – continuous, time-varying. These data will be available at t1 and t2.

*CYP variants* - dichotomous (yes/no), constant over the study period.

In addition to testing their significance as effect modifiers, we will also examine their relationship with the outcome variables (MBD, cytomorphology, proliferative index, etc) to validate known relationships. Proc Mixed for normal data and Proc GLMMIX for non-normal data in SAS 9.1 (Cary, North Carolina) will be used for analysis.

***Exploratory Aim 2: To examine the relationship between a low-dose tamoxifen regimen and clinical measures of efficacy and toxicity.***

For measures of clinical efficacy, we will document the occurrence of new breast cancer and DCIS diagnoses.

The assessment of clinical toxicity will include the following outcomes/measures:

- 1) incidence of uterine and other cancers during the study;
- 2) gynecological symptoms: any and the frequency of hot flashes, night sweats, vaginal discharge, vaginal bleeding or spotting, missed menstrual periods for pre-menopausal women, genital itching/irritation, and pain with intercourse, to be obtained from symptom log administered 10 times (baseline, days 28, 90, 180, 270, 365, 455, 540, 630, 730) ;
- 3) incident thromboembolic events (DVT, PE, TIA or stroke, and retinal vein thromboses);

4) incidence of cataract;

5) liver function abnormalities: total bilirubin, SGOT/AST, SGPT/ALT, measured at baseline, year 1, and year 2.

The *incidence* of new breast cancer, DCIS, non-breast malignancies, thromboembolic events, and cataract are expected to be low ( $\leq 5$  events per arm) during the study period given the sample size, based on statistics quoted in Investigational Brochure. Thus, we will initially compare the frequency of events by treatment group in a 2x2 table using the Fisher exact test, stratified on CYP2D6 status. We will also use poisson regression in cohort analysis to examine treatment differences in these outcomes adjusted for covariates, including CYP2D6.

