The presence/absence of gynecological symptoms (for each symptom mentioned above) will be compared between treatment groups using 2x2 tables using the Fisher exact test, stratified on CYP2D6 status. Logistic regression will be used to compare the frequency between treatments adjusted for covariates, including CYP2D6. Longitudinal analysis also will be conducted to compare the trends of the presence/absence of each of the reported gynecological symptoms over the 2 year period using the generalized linear mixed-effects model for binary outcomes.

For each liver function measure, a woman will be considered to have elevated liver function if the measurements at years 1 and/or 2 are above the upper limit of the institutional reference range and higher than her baseline pre-treatment level. These data will be coded such that those who are greater than 2-times the upper limit of the reference range will be considered to be clinically significant (grade 1 if asymptomatic and requiring no intervention; grade 2 if minimal/local/non-invasive intervention required). The frequency of women with elevated liver function measures will be compared between treatment groups using an exact test on 2x2 tables, stratified on CYP2D6. Logistic regression analysis will also be used to compare the frequency of elevated liver function between treatments, adjusted for covariates. Linear mixed-effects model for normally distributed data will also be used to compare the trends in liver function levels between the treatment groups. Procs MIXED and GLIMMIX will be used for longitudinal analysis of normally and non-normally distributed data, respectively. Poisson regression analysis will be conducted using Proc GENMOD, all in SAS 9.1 (Cary, North Carolina).

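### Symptom Log severity, including the Day 28 and Day 90 scores, has no stated Aim 2 model, and the 'any symptom' comparison has no rule for symptoms present before treatment

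*Combined protocol and SAP*

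**What the plan says.** Two instruments fall under patient-reported symptoms in Section 11.13: the NSABP questionnaire, described as a "quality of life (QOL) questionnaire to assess patient reported symptoms in response to hormonal interventions", and the Symptom Log, which contains the HEAL hormone-related scales. Their timing is left to the calendar: "Both questionnaires will be administered at baseline and during the two-year treatment period according to the study calendar". Section 10.3 lists the log among the safety and tolerability endpoints ("4. Symptom logs") and does not list the NSABP form.

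In Section 12.4, the Aim 2 paragraph on patient-reported symptoms models a 0-to-4 bother score from a questionnaire that it does not name: "The questionnaire will be administered every six months, for a total of five time points". It plans an unstructured mean model and piecewise models with a join at 6 months.

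Exploratory Aim 2 in the same section takes gynecological and vasomotor symptoms, as 'any' and as frequency, from the "symptom log administered 10 times (baseline, days 28, 90, 180, 270, 365, 455, 540, 630, 730". The test is stated as follows: "The presence/absence of gynecological symptoms (for each symptom mentioned above) will be compared between treatment groups using 2x2 tables", by Fisher's exact test. Logistic regression and a longitudinal mixed model for binary outcomes are added. Nothing there defines a new or worsened symptom, and baseline symptom status is not a named covariate.

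**The concern.** Tolerability is half of this trial's case for a low dose, and intolerance can show early. The Day 28 call in Section 9.4 exists to check tolerance and administers the log. Section 11.13 allows intolerable hot flashes to be managed during the study, so a Day 180 score may already reflect that management. A severity model whose first on-treatment value is Day 180 cannot show the early course. It also has no on-treatment severity value for a woman who has left by then, although one or two of her logs may exist.

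The second issue is separate. If a symptom reported before the first capsule counts towards 'any', the 2x2 comparison mixes pre-existing symptoms with those arising on treatment. The contrast between arms shrinks, and the reported rates overstate what happened on treatment. The liver measure in the same part of the plan avoids this: only years 1 and 2 count, and the value must exceed the woman's own pre-treatment level.

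**Working it through.** **1. The plan's count of five.** From the study calendar:

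| Instrument | Scheduled times | Count |
|---|---|---|
| NSABP Quality of Life Form | baseline, 180, 365, 540, 730 | 5 |
| Symptom Log | baseline, 28, 90, 180, 270, 365, 455, 540, 630, 730 | 10 |

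The five in Aim 2 reproduces for the NSABP form. The ten in Exploratory Aim 2 reproduces for the log.

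**2. Two readings of the unnamed questionnaire.** If it is the NSABP form, the schedule is right, but the log, which is the listed endpoint, has no Aim 2 severity analysis. If it is the log, Aim 2 contradicts the calendar and Exploratory Aim 2. On both readings the log scores at Days 28, 90, 270, 455 and 630 (five of nine on treatment) enter no stated severity model. With five points, nothing is observed between baseline and the 6-month join. Using all ten logs gives 9 time-by-treatment terms in the unstructured model in place of 4, and two on-treatment values before Day 180.

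**3. What Exploratory Aim 2 covers.** Its list is hot flashes, night sweats, discharge, bleeding or spotting, missed periods, itching or irritation, and pain with intercourse. Section 11.13 also gives the log incontinence, cognitive/mood and weight gain/appearance scales. These are outside the list, so they have no stated model.

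**4. Size of the dilution.** Section 12.5 gives prevalence rates of 35% v 55% for vaginal discharge and 68% v 80% for hot flashes. Assume these are on-treatment rates p. Let s be the share of women without the symptom on treatment who reported it at baseline, equal in both arms. The documents do not give s.

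'Any' rate = p + (1 - p)s; difference = (1 - s)(p2 - p1). Power is two-sided Fisher exact at 0.05 by enumeration, 115 per arm.

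| s | Discharge | Difference | Power | Hot flashes | Difference | Power |
|---|---|---|---|---|---|---|
| 0 | 35.0 v 55.0 | 20 | 84.5% | 68.0 v 80.0 | 12.0 | 48.8% |
| 10% | 41.5 v 59.5 | 18 | 75.8% | 71.2 v 82.0 | 10.8 | 43.3% |
| 20% | 48.0 v 64.0 | 16 | 65.3% | 74.4 v 84.0 | 9.6 | 37.8% |
| 30% | 54.5 v 68.5 | 14 | 53.6% | 77.6 v 86.0 | 8.4 | 32.3% |

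The plan states 90% power for discharge and 41% for hot flashes. The 41% reproduces at 94 per arm (40.6%). The 90% does not reproduce with a two-sided test at 94 (74.2%) or at 115 (84.5%), so the table starts from the computed values.

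**5. The denominator matters for the remedy.** Suppose instead that 35% v 55% is new onset among women free of the symptom at baseline, and that a fraction b have it at baseline. The literal 'any' rate is b + (1 - b)p, with the same differences of 18, 16 and 14 points at b = 10%, 20% and 30%. New onset counted over all randomised women is (1 - b)p. Its difference is also 0.20(1 - b), so nothing is recovered. Restricting to women free of the symptom returns 20 points on 115(1 - b) per arm, rounded down:

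| b | Literal 'any', n = 115 | New onset over all, n = 115 | New onset among symptom-free |
|---|---|---|---|
| 10% | 75.8% | 76.2% | 79.2% (n = 103) |
| 20% | 65.3% | 66.7% | 72.7% (n = 92) |
| 30% | 53.6% | 57.7% | 66.1% (n = 80) |

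The gain comes from conditioning on baseline status, not merely from relabelling events as new.

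**The case against.** The strongest reply is that the sentence on five time points is correct. It fits the NSABP form's calendar row exactly, and Section 11.13 presents that form as a symptom instrument. This stands: the sentence is not shown to be an error. What remains is that the instrument is unnamed and the listed endpoint lacks a severity model.

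A reader might infer that early symptoms are lost altogether. The documents do not support that. Exploratory Aim 2 puts the Day 28 and Day 90 logs into a binary longitudinal model for the listed symptoms. Early intolerance also shows in the three-monthly pill counts, the comparison of voluntary withdrawals and the Study End Form. Section 10.0 says that women who begin treatment are accounted for in patient-reported summaries, evaluable or not. Only early severity and the unlisted log scales lack a stated model.

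A reader might also infer that both features favour tamoxifen. That goes too far. Randomisation should make baseline symptoms equal in expectation, so counting them pulls the comparison towards no difference while raising the tamoxifen arm's absolute rate. Nor is the direction of the missing early severity established.

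Finally, listing baseline in Exploratory Aim 2 may describe collection only. The liver tests are listed there with a baseline too, yet only years 1 and 2 count as events. That is fair: inclusion of baseline is the literal reading, not an explicit event rule. But the liver measure is then given a rule and the symptom measure is not. The binary longitudinal model is not affected, and the aim is declared exploratory.

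**Conclusion.** The point holds as a gap in specification with a cheap remedy. Five of the nine on-treatment Symptom Log severity assessments, including both before Day 180, and three log scales have no stated model, although the log is the listed tolerability endpoint. This assumes that the log records a graded score; its response scale is not given in the protocol text.

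The 'any symptom' comparison lacks a post-baseline rule. On the literal reading, the difference between arms shrinks by the factor (1 - s), in both arms alike, and both absolute rates rise. The 18, 16 and 14 points for discharge are illustrations over an assumed range; the documents give no baseline symptom prevalence. That a third of the cohort is expected to be postmenopausal makes some baseline vasomotor symptoms plausible but does not supply a figure, least of all for discharge. The effect is confined to the 2x2 'any' comparison and analyses built on the same definition.

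**What to change.** In the Aim 2 paragraph of Section 12.4, name the instrument and keep five time points for the NSABP form. Add a mixed-model analysis of Symptom Log severity at all ten scheduled times, with baseline as reference and time terms that use Days 28 and 90. Include the incontinence, cognitive/mood and weight gain/appearance scales.

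In Exploratory Aim 2, count only the nine post-baseline logs and condition on baseline. Either compare new onset among women without the symptom at baseline, and worsening over own baseline score among the rest, or stratify or adjust the post-baseline 'any' comparison for baseline status. Baseline status is fixed before randomisation, so these comparisons remain randomised. Counting new onset over all randomised women is not enough, as the second table shows.

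The cost is analysis-plan wording and a little more programming. No visit, form or participant is added. The wording should be settled before unblinding.

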#### A. Patient demographics.

The following variables are known to affect breast cancer risk and MBD.

*Attained age* – continuous, time-varying variable.

*Menopausal status* – status at study enrollment (premenopausal or postmenopausal, as defined in Section 5.0) will be considered as constant over the study period. We will also consider trichotomized status (pre-menopausal, typical post-menopausal, and early post-menopausal), constant over the study period. Menopause will be defined as “early” if onset was before age 50.

*Prior hormone use* – categorical variable (estrogen plus progestin menopausal hormone therapy, estrogen-only menopausal hormone therapy, hormonal contraception and/or fertility drugs, no prior hormonal therapy). We will also consider duration of use, as a continuous and dichotomous variable (5+ years, <5 years); and most recent use (within 1 year, >1 year).

*Body mass index (BMI)* – continuous, time-varying variable. It will also be grouped into ordinal categories: underweight (<19), normal weight (19-24), overweight (25-29), obese (30-39), morbidly obese (40+).

*Personal history of benign breast disease* – dichotomous (yes/no), constant over the study period. We will also examine whether the number of prior breast biopsies, and the presence of atypia or LCIS on a prior biopsy further modifies the intervention effect.

*Family history of cancer* – dichotomous (yes/no), constant over the study period. We will also examine the frequency of the following classifications: 0 = no family members with breast cancer; 1 = one or more first or secondary degree relative(s) with BC all diagnosed at 50+ years of age; 2= one first or second degree relative with BC diagnosed

before age 50 (or two, but on different sides of the family); 3 = two or more first and/or second degree relatives with BC diagnosed before age 50 and/or ovarian cancer on the same side of the family; 4 = carrier of a germline mutation in a highly penetrant BC susceptibility gene (BRCA1, BRCA2, PTEN, p53), or a known mutation in one of these genes in the patient's family and patient has not had genetic testing. If this results in sparse cells, we will consider collapsing them: A = no family history, B = some family history (group 2 above), and C = strong family history (groups 3 and 4 above). We will also examine if the number of first & second degree relatives (constant over the study period) is a significant effect modifier.

#### B. Clinical primary cancer treatment characteristics.

The following variables are known to influence breast cancer risk among radiation exposed CAYAC survivors.

*Chest radiation dose* – continuous, time-invariant. We will also dichotomize dose levels as described in Section 12.3.

*Age at exposure to chest radiation* – continuous, time-invariant. We will also categorize as described in Section 12.3.

*Latency from radiation therapy* – continuous, time-varying. We will examine if intervention effects vary by time since exposure to therapeutic radiation.

*Pelvic radiation* – continuous, time-invariant. Depending on the range of doses, we will also consider dichotomizing or categorizing the dose levels.

*Alkylator containing chemotherapy regimen* – dichotomous (yes/no), time-invariant.

